2.1 Hypotheses

Kidney and liver transplant recipients who had a negative or low (≤ 2500 U/mL) anti-SARS-CoV-2 S response (using the Roche Elecsys® assay) to a completed primary series of the Moderna COVID-19 Vaccine or the Pfizer-BioNTech COVID-19 Vaccine will develop an enhanced SARS-CoV-2 antibody response after receiving a dose of study vaccine, with or without reduction of their maintenance transplant immunosuppression regimen.

Temporary reduction of maintenance immunosuppression as directed in this protocol will result in higher fold increase in antibody titer than achieved in those who do not have IS reduction, without an increased risk of alloimmune events (rejection or development of dnDSA).

2.2 Primary Objective(s)

The primary objective of this study is to elicit a more robust anti-SARS-CoV-2 S level in kidney and liver transplant recipients who had an undetectable or low (≤ 2500 U/mL) level of antibody after completing a primary series of mRNA COVID-19 vaccine. Antibody titers in response to the study dose of vaccine will be evaluated 30 days following vaccine administration and will be measured using the Roche Elecsys® anti-SARS-CoV-2 S. All participants with measurable SARS-CoV-2 antibody titers will also have neutralizing antibody titers and further quantification and characterization of antibody using the best available assay(s).

2.3 Secondary Safety Objective(s)

To determine the incidence of adverse events (AEs) and serious adverse events (SAEs), including reactogenicity, following the additional dose of vaccine.

To determine the incidence of alloimmune events (e.g., allograft rejection and development of de novo DSA) following the immunosuppression reduction and/or the additional dose of vaccine.

2.4 Secondary Efficacy Objectives

To determine the incidence of symptomatic or asymptomatic SARS-CoV-2 infection in the 12 months following the additional dose of vaccine.

2.5 Secondary Immunogenicity Objectives

To assess whether responses to additional doses of COVID-19 vaccine are improved by temporary reduction or withholding of immunosuppressive medications around the time of vaccine.

To assess whether response to an additional dose of COVID-19 vaccine is associated with clinical phenotype (e.g., age, organ type, time post-transplant, immunosuppressive regimen).

To evaluate durability of response over 1-year in those who have an antibody response to the additional dose of vaccine.

2.6 Exploratory Objectives

To identify immunologic correlates of vaccine response.

To evaluate immune activation in response to the vaccine.

To assess whether timing between vaccine doses is associated with differential antibody response to vaccination.

To assess whether there is a difference in antibody levels among those receiving additional doses of Pfizer versus Moderna vaccination.

3. Study Design

3.1 Description of Study Design

A randomized, open-label multi-site trial designed to induce an enhanced antibody response to SARS-CoV-2 in kidney and liver transplant recipients who have a negative or low (≤ 2500 U/mL) antibody response (using the Roche Elecsys® anti-SARS-CoV-2 S) following a completed primary series of mRNA COVID-19 vaccine. Participants will be randomized to receive a dose of COVID-19 vaccine (Moderna or Pfizer-BioNTech), with or without immunosuppression (IS) reduction.

[figure not shown]

Figure 1. Study Design Diagram

3.2 Primary Endpoint

The primary endpoint is the -fold increase in antibody titer (using the Roche Elecsys® anti-SARS-CoV-2 S assay) from before receiving the study dose of vaccine to 30 days after the study dose of vaccine.

3.3 Secondary Endpoints

3.3.1 Secondary Safety Endpoints

Local and systemic vaccine reactogenicity and/or allergy
Serious adverse events occurring during the 30 days following the additional dose of vaccine
Treated acute cell-mediated and/or antibody-mediated allograft rejection (clinical or biopsy-proven) within 60 days following the additional dose of vaccine
Development of de novo donor-specific anti-HLA antibody within 90 days of the vaccine
Graft loss within 60 days of the vaccine
Death within 60 days of the vaccine

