6.7 Immunosuppression Reduction

6.7.1 Immunosuppression (IS) Reduction

Participants on a tacrolimus-based regimen that includes MMF (or equivalent), with or without corticosteroid:

MMF (or equivalent) will be withheld for five days prior to and 2 weeks following vaccine administration. During the interval that MMF is withheld, no adjustments will be made to the CNI or corticosteroid dose.

Participants on a tacrolimus based regimen with a trough level ≥ 5 ng/mL, with or without ≤ 5 mg Prednisone (or equivalent) and no MMF or other antimetabolite

Reduce CNI by 25% of starting dose for 5 days prior to and 2 weeks following vaccine administration.

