12.2 Definitions

12.2.1 Adverse Event (AE)

Any untoward or unfavorable medical occurrence associated with the subject's participation in the research, whether or not considered related to the subject's participation in the research (modified from the definition of adverse events in the 1996 International Conference on Harmonization E-6 Guidelines for Good Clinical Practice) (from OHRP "Guidance on Reviewing and Reporting Unanticipated Problems Involving Risks to Subjects or Others and Adverse Events (1/15/07)" <http://www.hhs.gov/ohrp/policy/advevntguid.html#Q2>)

For this study, adverse events will be considered for association with the additional dose of COVID-19 vaccine and study mandated procedures as follows:

Vaccine Administration (Moderna COVID-19 Vaccine (monovalent, bivalent, and 2023-2024 formula as per protocol version), Pfizer-BioNTech COVID-19 Vaccine (monovalent, bivalent, and 2023-2024 formula as per protocol version)

All AEs occurring within 30 days following a single COVID-19 vaccine dose and SAEs up to 6 months post vaccine administration.

Study mandated procedures:

Any AE occurring within 24 hours of a protocol mandated blood draw
Any AE occurring within 24 hours of a protocol mandated nasal swab
Any AE occurring within 24 hours of an oral fluid collection
Any AE occurring during the period from the onset of immunosuppression reduction until 30 days after return to full immunosuppression and SAEs up to 6 months post return to full immunosuppression.

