12.4 Collection and Recording of Adverse Events

12.4.1 Collection Period

Adverse Events temporally associated (24 hours) with the research blood draws and nasal swabs will be collected from the time of the screening visit until a subject completes study participation.

COVID-19 Vaccine Dose Alone: Adverse Events as defined in Section 12.2.1 will be collected for 30 days following COVID-19 vaccine administration. Serious Adverse Events will be collected for 6 months following vaccine administration.

COVID-19 Vaccine Dose plus IS Reduction: All Adverse Events will be collected in those who undergo immunosuppression reduction occurring from the onset of IS reduction until 30 days after return to full immunosuppression. Serious Adverse Events will be collected for 6 months post onset of IS reduction.

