13.2 Endpoints/Outcomes

The primary endpoint is the proportional increase in antibody titer U/mL (using the Roche Elecsys® anti-RBD assay) at 30 days after the study dose of vaccine. Negative or very low antibody responses (<10 U/mL) will be imputed to 10 U/mL, to reduce the influence of measurement error on the proportional increase calculation among individuals with very low titers. Secondary safety endpoints include: local and systemic vaccine reactogenicity and/or allergy; serious adverse events occurring during the 30 days following the additional COVID-19 vaccine dose; treated acute cell-mediated and/or antibody-mediated allograft rejection (clinical or biopsy-proven) within 60 days following the COVID-19 vaccine dose; development of de novo donor-specific anti-HLA antibody within 90 days of the vaccine; graft loss within 60 days of the vaccine; and death within 60 days of the vaccine. Secondary efficacy endpoints include: SARS-CoV-2 PCR positivity; symptomatic COVID-19; COVID-19 requiring hospitalization; and longitudinal changes in SARS-CoV-2 antibody response during the study.

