13.7 Sample Size Considerations

Comparison of the primary endpoint will use a two-sided ranksum test. There will be 400 patients, 200 per treatment group. Power calculations assume an α of 0.05. The power of the study will depend on the distribution of -fold changes in each group.

We ran simulations in which -fold changes are log-normally distributed, and computed power based on the ratio of -fold change between the two groups. For example, if the average -fold increase in one group is a twofold increase and in the other group, a threefold increase, the ratio of -fold change is $3/2$ or 1.5. (This does not mean that each individual in one group experienced a twofold increase; some individuals would experience a greater increase, and some a smaller increase.) In the simulation, with an N of 400, generally the study has 80% power to detect a difference of 20% (e.g. mean 2.5-fold increase in one group vs 3-fold increase in the other.)

14. Identification and Access to Source Data**14.1 Source Data**

Source documents and source data are the original documentation where subject information, visits consultations, examinations and other information are recorded. Documentation of source data is necessary for the reconstruction, evaluation and validation of clinical findings, observations, and other activities during a clinical trial.

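### All-cause serious adverse events after Day 30 have no between-arm endpoint, although the plan collects them for about six months

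*Combined protocol and SAP*

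**What the plan says.** Section 3.3.1 lists the endpoint as "Serious adverse events occurring during the 30 days following the additional dose of vaccine". Section 13.2 repeats the window: "serious adverse events occurring during the 30 days following the additional COVID-19 vaccine dose".

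Collection runs longer. For the vaccine-alone arm, section 12.4.1 states "Serious Adverse Events will be collected for 6 months following vaccine administration". For the reduction arm the same section states "Serious Adverse Events will be collected for 6 months post onset of IS reduction", whereas section 12.2.1 counts "SAEs up to 6 months post return to full immunosuppression".

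Both arms receive vaccine, so the randomised contrast is the reduction. For participants on MMF, section 6.7.1 reads "MMF (or equivalent) will be withheld for five days prior to and 2 weeks following vaccine administration", and the CNI reduction has the same timing.

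Other listed endpoints run past Day 30. Treated rejection, graft loss and death run to Day 60 and de novo DSA to Day 90 (3.3.1). COVID-19 hospitalisation has no 30-day limit (3.3.2).

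Section 13.4.3 assigns Fisher's exact test to binary secondary endpoints. It assigns an incidence rate difference with a 95% CI to *severe*, not serious, adverse events, and gives no time window.

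**The concern.** A 30-day window suits reactions to a vaccine. It suits the randomised intervention less well, because it closes about 16 days after immunosuppression is restored. The plan itself treats the period of concern as longer. Graft function is monitored for a month after the original regimen resumes (8.3.3). Ordinary adverse events in the reduction arm are collected until 30 days after that point (12.4.1). Both run to about Day 44. The SAE endpoint therefore closes before the reduction arm's own routine AE collection does.

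All-cause SAEs are the broadest comparison of harm between the arms. At stake are later admissions that fit none of the narrower endpoints. These events will be in the database without a prespecified between-arm analysis. In an open-label trial, a window chosen after results are visible would carry less weight.

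**Working it through.** **Plan's own figure.** The documents state no SAE rate and no power for SAEs. The only power figure (80%, section 13.7) concerns the antibody endpoint, so there is nothing to reproduce here.

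**Windows.** Take 6 months = 365.25/2 = 182.6 days, with vaccine on Day 0 and reduction from Day -5 to Day 14.

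- SAE endpoint after reduction ends: 30 - 14 = 16 days.
- Vaccine-alone arm: collection from Day 0 to about Day 183. Share outside the endpoint: (182.6 - 30)/182.6 = 83.6%.
- Reduction arm, section 12.4.1: Day -5 to 182.6 - 5, about Day 178. Share outside: 83.6%. This includes the 5 days before vaccination.
- Reduction arm, section 12.2.1: Day -5 to 14 + 182.6, about Day 197, a length of 201.6 days. Share outside: (201.6 - 30)/201.6 = 85.1%.
- The two end dates for the reduction arm differ by 5 + 14 = 19 days.

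**What captures SAEs after Day 30**

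| Event after Day 30 | Between-arm endpoint |
|---|---|
| Treated rejection, graft loss, death | yes, to Day 60 |
| COVID-19 hospitalisation | yes, no 30-day limit |
| Non-COVID infection admission | none |
| Admission for graft dysfunction not treated as rejection | none |
| Any other SAE | none, unless the windowless *severe* analysis in 13.4.3 was meant to cover it |

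**Sensitivity to a doubling.** Inputs from section 13.7: "There will be 400 patients, 200 per treatment group" and "Power calculations assume an α of 0.05". Two-sided testing is assumed for SAEs, with no dropout. The control rate r per 30 days is an assumption: 1%, 2% or 3%.

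*Exact Fisher test (participants with an SAE).* Power is the sum of the binomial probabilities of all 2×2 tables with p < 0.05. The 30-day row doubles the risk; the six-month rows use a constant hazard over 182.6/30 = 6.09 periods.

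| Scenario | r = 1% | 2% | 3% |
|---|---|---|---|
| 30 days, risk doubled | 4% | 13% | 23% |
| 6 months, hazard doubled throughout | 44% | 75% | 89% |
| 6 months, excess confined to first 30 days | 4% | 6% | 8% |

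*Rate difference (Poisson, Wald CI excluding 0).* Let w be the window and e the duration of the doubled rate, both in 30-day units, and E = 200·r·e. Then power = Φ(E/√(2·200·r·w + E) - 1.96).

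At r = 2%:
- 30 days: E = 4; 4/√(8 + 4) = 1.155; Φ(-0.805) = 21%.
- 60 days, excess to Day 60: E = 8; 8/√(16 + 8) = 1.633; Φ(-0.327) = 37%.
- 6 months, excess throughout: E = 24.35; 24.35/√(48.7 + 24.35) = 2.849; Φ(0.889) = 81%.
- 6 months, excess to Day 60 only: E = 8; 8/√(48.7 + 8) = 1.062; Φ(-0.898) = 18%.

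For r = 1% to 3% these four become 13-29%, 21-52%, 52-94% and 11-26%.

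**Outside the assumed range.** By Fisher, 30-day power for a doubling reaches 50% at a control rate of about 6.1% and is 77% at 10%. A low bound comes from the registry expectations in section 11.5: 5-6 rejections, 6-7 graft losses and about 5 deaths make 16-18 events in 400 participants. If the course of the study means about 12 months, that is 16/400 × 30/365.25 = 0.33% to 18/400 × 30/365.25 = 0.37% per 30 days. At 0.35%, Fisher power is 0.2% at 30 days and 14% at six months with a persistent excess. These events may overlap, and they are only part of all SAEs.

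**The case against.** Collecting SAEs for longer than one endpoint's window is not in itself an error. The harms most specific to reduction, rejection and de novo DSA, already have longer windows. Planned DSMB reviews receive a listing of all reported AEs and SAEs, including at database lock (12.7.2.1). The Grade 4 or 5 pausing rule has no 30-day limit (11.5), and the safety objective has none either (2.3). All of this stands. It shows that late SAEs are seen, but a listing is not a prespecified comparison between arms.

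A reader might infer that no SAE after Day 30 enters any endpoint. The documents do not support that: deaths, graft losses and treated rejections count to Day 60, and COVID-19 hospitalisations count beyond Day 30.

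A reader might also infer that a doubling of SAEs would usually be missed. That depends on a rate the documents do not give. By Fisher it holds below about 6% per 30 days and fails above. The low power also reflects few events at 200 per arm, not the window alone.

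Nor is a longer window always better. Reduction ends about Day 14, so a transient excess is plausible, and six months of follow-up would dilute it.

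**Conclusion.** The point holds in limited form, as a low-cost improvement rather than a flaw that threatens the trial. All-cause SAEs after Day 30 have no clearly named between-arm endpoint, and about five-sixths of the SAE follow-up time lies outside the 30-day window. This share describes time, not events.

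Sections 3.3.1, 13.2, 12.4.1 and 6.7.1 establish the gap without any assumed rate. The power figures do rest on the assumed 1-3% per 30 days, and the six-month gain needs the excess to persist. They illustrate sensitivity and should not be quoted as the trial's power.

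Two wording problems stand in the way of a six-month comparison. Section 13.4.3 names *severe* events where *serious* may be meant, and sections 12.2.1 and 12.4.1 give different ends of collection for the reduction arm.

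**What to change.** 1. In sections 3.3.1, 13.2 and 13.4.3, keep the 30-day SAE endpoint. Add all-cause SAEs from vaccination to Day 60, and to a common cut-off near six months that both arms reach (about Day 178 under section 12.4.1).
2. Report each as an incidence rate difference with 95% CI, reading the interval as the precision achieved. Use person-time denominators: under the schedule footnotes, participants with a positive Day 0 swab are followed only to Day 30.
3. List reduction-arm SAEs from Day -5 to Day 0 separately; an endpoint that starts at vaccination leaves them out.
4. State in section 13.4.3 whether *severe* or *serious* is meant, and give the window.
5. Reconcile sections 12.2.1 and 12.4.1 on the end of SAE collection in the reduction arm, then fix the common cut-off.
6. Settle these choices before comparative results are seen.

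Cost: protocol and SAP wording, two more table rows and a short listing. The SAEs are already being collected. The downside is that longer windows contain more background events and can hide a short-lived excess, so the 30-day result should stay alongside.

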13.4 Analysis Plan

13.4.1 Analysis Populations.

For the primary outcome and each secondary outcome, the analysis population will consist of all individuals with a measurement for that outcome, in an intent-to-treat framework.

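### SAE and treated-rejection endpoints start at the vaccine, five days after the randomised intervention begins, and no timed safety endpoint has a time zero for participants never vaccinated

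*Combined protocol and SAP*

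**What the plan says.** - **Endpoints (Section 3.3.1, repeated in the Synopsis and Section 13.2).** SAEs: "Serious adverse events occurring during the 30 days following the additional dose of vaccine". Rejection: "Treated acute cell-mediated and/or antibody-mediated allograft rejection (clinical or biopsy-proven) within 60 days following the additional dose of vaccine". De novo DSA: "Development of de novo donor-specific anti-HLA antibody within 90 days of the vaccine". Graft loss: "Graft loss within 60 days of the vaccine". Death has the same 60-day wording as graft loss.
- **Objective (Section 2.3).** Alloimmune events are to be assessed "following the immunosuppression reduction and/or the additional dose of vaccine".
- **Intervention (Section 6.7.1).** MMF or its equivalent "will be withheld for five days prior to and 2 weeks following vaccine administration". The CNI reduction for participants without an antimetabolite has the same timing. Section 13.3 places randomisation before the vaccine.
- **Collection (Section 12.4.1).** In the reduction arm, AEs are collected "from the onset of IS reduction until 30 days after return to full immunosuppression", and SAEs for six months from onset of reduction. In the vaccine-alone arm both start at the vaccine, apart from events tied to blood draws and swabs.
- **Analysis (Section 13.4.1).** For each outcome "the analysis population will consist of all individuals with a measurement for that outcome", under an intent-to-treat label.
- No section gives a substitute Day 0 for someone randomised but not vaccinated.

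**The concern.** Both arms receive the vaccine, so the randomised contrast is the reduction, and exposure to it begins on Day -5. Section 2.1 hypothesises that reduction brings no added alloimmune risk. Two endpoints that bear on that hypothesis ignore the first days of exposure. Only the reduction arm has a study intervention before Day 0, so harm it causes in those days can be lost only there, and the loss favours the hypothesis.

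The second gap is the missing time zero for participants never vaccinated. If the reason for not vaccinating is related to assignment or to early harm, leaving these people out undoes the randomisation for the safety comparison. Section 13.4.3 compares severe adverse events by an incidence rate difference but does not say when person-time starts, so it does not fill either gap.

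**Working it through.** The plan states no figure on this point, so there is nothing to reproduce. The check sets the texts side by side and then sizes the gap.

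1. **Which endpoints exclude Days -5 to -1?** SAE and rejection are worded as *following* the dose, so they exclude those days. Graft loss and death are worded as within 60 days *of* the vaccine, with no direction, so they are ambiguous. For DSA, the schedule (Appendices 1 to 3, kidney only) has a screening sample, then nothing until Week 4. Antibody arising before the vaccine in a vaccinated kidney recipient would first be seen at Week 4, and would count.

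2. **Days outside the clock.** Reduction lasts 5 + 14 = 19 days, of which 5/19 = 26% precede the vaccine. The five days are 5/(5 + 30) = 14.3% of a Day -5 to Day 30 SAE window and 5/(5 + 60) = 7.7% of a Day -5 to Day 60 rejection window. These are shares of time, not of events.

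3. **Expected rejections in the five days.** Inputs: 5-6 background rejections over the study (Section 11.5); 400 participants, 200 per arm (Section 13.7). With a constant hazard, k events, time base T days and hazard multiple m:

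   E = m × k / (400 × T) × 200 × 5

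   The documents do not state T. I bracket it with 365 days (the 12-month follow-up) and 60 days (the rejection window).

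   | T (days) | m | k = 5 | k = 6 |
   |---|---|---|---|
   | 365 | 1 | 0.03 | 0.04 |
   | 60 | 1 | 0.21 | 0.25 |
   | 365 | 3 | 0.10 | 0.12 |
   | 60 | 3 | 0.63 | 0.75 |

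   Under a Poisson model, the chance of at least one such event runs from about 3% (T = 365, m = 1, k = 5) to about 53% (T = 60, m = 3, k = 6). The multiple of three is borrowed from the excess that the Section 11.5 pausing rules look for. It is not a forecast. The documents give no SAE rate, so no SAE count can be derived.

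4. **Never vaccinated.** All five timed endpoints are measured from the vaccine, and so are the follow-up visits in Section 8.3.3. An unvaccinated participant in either arm has no date from which to count. The documents give no rate. If 1%, 2% or 5% of 400 were unvaccinated, that would be 4, 8 or 20 people.

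**The case against.** The strongest reply has four parts.

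- **Rejection is unlikely to be lost in practice.** The endpoint is treated rejection. In Appendix 3 the first graft laboratory tests after reduction starts are on Day 0, and Section 6.12 repeats an abnormal value in 1-3 days. Rejection found through scheduled monitoring would therefore be treated on or after Day 0. This stands, and it means the counts above are more likely too high than too low. It does not cover an off-schedule diagnosis treated before Day 0, nor SAEs.
- **The harm is visible.** Events are collected from onset of reduction, the DSMB sees all reported AEs and SAEs, and the rejection, graft-loss and mortality pausing rules carry no vaccine clock. This also stands. The gap lies in endpoint definition, not in surveillance.
- **The documents do not exclude the never-vaccinated outright.** Section 13.4.1 invokes intent-to-treat and does not say that a rejection observed in an unvaccinated participant is not a measurement. That is fair: the text is silent. But a window with no start cannot be applied, and the analyst would have to invent a rule after seeing the data.
- **The numbers are small.** They are. With 5-6 rejections expected in the whole trial, however, one misplaced event is visible in a comparison of 200 against 200.

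**Conclusion.** The point holds for the SAE and treated-rejection endpoints, which are narrower than the objective in Section 2.3, and for the missing time zero of participants never vaccinated. The expected loss is a fraction of one rejection: 0.03 to 0.25 at background hazard and 0.10 to 0.75 at three times that, assuming a constant hazard and a time base of 60 to 365 days. The size of the never-vaccinated group is unknown.

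A reader might infer that pre-vaccine events count in no endpoint at all. The documents do not support that. Early DSA would be counted at Week 4 in vaccinated kidney recipients, the graft-loss and death wording is open in direction, and a rejection that begins before the vaccine but is treated afterwards may count, since no event-date rule is given. A reader might also infer that the never-vaccinated gap affects the reduction arm alone. It affects both, because controls too are randomised before the vaccine. Only the loss of pre-vaccine harm from the intervention is confined to the reduction arm. This should be corrected because the exclusion runs one way and is cheap to remove, not because it is likely to be large.

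**What to change.** - Start the SAE, rejection, de novo DSA, graft-loss and death windows at randomisation in both arms, and run them through Day 30, 60 or 90 after vaccination as now.
- Record a scheduled vaccination date at randomisation, and use it as Day 0 for participants not vaccinated.
- Include all randomised participants in these analyses, and state which date (onset, diagnosis or treatment) places an event in its window.
- State that person-time for the rate difference in Section 13.4.3 starts at randomisation.
- Keep the vaccine-anchored windows as a secondary table.

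The cost is endpoint wording, SAP programming and one change in data collection: SAE and event collection in the vaccine-alone arm must begin at randomisation instead of Day 0 (Section 12.4.1), which adds a short event question at Day 0. If the interval from randomisation to vaccination differs between arms, the windows will differ in length, so that interval should be reported by arm. Participants with a positive Day 0 swab are followed only to Day 30 (footnote 7 of Appendices 2 and 3), so the SAP must also say how their 60- and 90-day windows are handled. Nothing here changes treatment.
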